8.3. Safety Assessments

Planned timepoints for all safety assessments are provided in Table 3 and Table 4.

The investigator(s) and the sponsor will review the safety data.

Safety will be evaluated by monitoring all AEs and clinically significant abnormalities identified through physical examinations, vital signs, and laboratory assessments. Such events and laboratory and AE toxicities will be graded according to NCI CTCAE v5.0 (or higher). Laboratory safety assessments will include routine monitoring of hematology and blood chemistry and tests of immunologic parameters.

Adverse events, pregnancies, concomitant medications, procedures, and hospitalizations will be recorded from signing the ICF until 90 days after the last dose of treatment or until the start of new anticancer therapy, whichever occurs first. Participants who relapse or progress and/or

prematurely discontinue the study treatment will continue to be followed for SPM throughout the study.

Adverse events and concomitant medications terms will be coded using MedDRA and a validated medication dictionary.

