8.8. End of Treatment and/or Early Treatment Discontinuation

The EOT visit will be performed at the time the decision is made to discontinue study treatment or after the participant has completed the prescribed treatment regimen (Cycle 12 Day 28). If the EOT visit coincides with a regular study visit, the EOT evaluations will supersede those of that scheduled visit, and the data should be entered in the EOT visit in the eCRF. The participant should be encouraged to return for the follow-up visits.

See Table 3 and Table 4 for the list of assessments be performed at the EOT visit.

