9.4. Reporting of Serious Adverse Events

Regardless of suspected causality (eg, relationship to study treatment or study procedure[s]), all SAEs occurring after the participant has signed the ICF through completion of the study *or* until the participant starts a new anticancer therapy (whichever occurs earlier) must be reported to the sponsor (or designee) within **24 hours** of learning of its occurrence, unless otherwise specified by the Protocol. The investigator will submit any updated SAE data to the sponsor (or designee) immediately, without undue delay but not later than within 24 hours of it being available. For Japan, this information must also be reported immediately to the head of the study site in Japan.

Investigators are not obligated to actively seek SAE information after the EOT visit. If the investigator learns of any SAE, including a death, at any time during this period, and he/she considers the event to be reasonably related to the study treatment or study participation, then the investigator must notify the sponsor (or designee) within 24 hours of becoming aware of the event.

After the initial AE/SAE report, the investigator is required to proactively follow each participant at subsequent visits/contacts. All SAEs and AESIs (as defined in Section 9.5.1) will be followed until resolution, stabilization, the event is otherwise explained, or the participant is lost to follow-up (as defined in Section 7.3).

Prompt notification by the investigator to the sponsor regarding an SAE is essential so that legal obligations and ethical responsibilities towards the safety of participants and the safety of a study treatment under clinical investigation are met.

If the SAE is not documented in the RSI of the IB or product information for study treatment (new occurrence) or marketed products, respectively, and is thought to be related to the study treatment, the sponsor or its designee may urgently require further information from the investigator for expedited reporting to health authorities. The sponsor or its designee may need to issue an Investigator Notification to inform all investigators involved in any study with the same drug that this SAE has been reported. SUSARs will be collected and reported to the competent authorities and relevant ethics committees in accordance with Directive 2001/20/EC or as per national regulatory requirements in participating countries.

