10.4.2. Safety Analyses

Safety analyses will be conducted for the SAF. No formal statistical testing will be performed.

[figure not shown]
All TEAEs, clinical laboratory measurements, vital sign measurements, and abnormal ECGs will be summarized by treatment group. Quantitative safety variables and their changes from baseline (laboratory and vital signs) will be summarized with descriptive statistics. Abnormal values outside of established ranges will be flagged and tabulated based on predefined criteria.

Measures of exposure (eg, days of exposure, dose intensity) of tafasitamab/placebo, lenalidomide, and rituximab will be summarized descriptively.

Adverse events will be coded by the MedDRA dictionary and severity of AEs will be based on the NCI CTCAE v5.0 using Grades 1 through 5. A TEAE is defined as an AE either reported for the first time or worsening of a pre-existing event on or after first dose of study treatment and within 90 days of the last administration of study treatment. Number (%) of participants reporting any TEAEs, any serious TEAEs, any Grade 3 or higher TEAEs, any treatment-related TEAEs, any treatment-related serious TEAEs, any treatment-related Grade 3 or higher TEAEs, any fatal TEAEs, and any TEAEs leading to treatment interruption/delay/dose reduction/discontinuation will be tabulated by MedDRA system organ class and preferred term. Data listings will include all AEs regardless of their timing to study drug/treatment administration.

The clinical laboratory data will be analyzed using summary statistics; no formal treatment group comparisons are planned. In addition, distributions of key laboratory parameters may be plotted over time; these values will also be classified into CTCAE toxicity grades when applicable, and tabulated.

Descriptive statistics and mean change from baseline will be determined for vital signs at each assessment time. The abnormal values for participants exhibiting vital sign abnormalities will be listed.

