4.1.5. Cycle Length and Duration

The scheduled cycle length is 28 days.

Cycle 1 Day 1 is the day that the first dose of study drug (tafasitamab/placebo, lenalidomide, or rituximab) is administered. The actual Day 1 of subsequent cycles will correspond with the first day of administration of tafasitamab/placebo, lenalidomide, or rituximab in that cycle. The date of the Day 1 of subsequent cycles recorded on the eCRF will be used as the Day 1 of the subsequent cycles.

The study consists of the screening period (\leq 28 days), treatment period (up to twelve 28-day cycles for tafasitamab/placebo and lenalidomide, and up to five 28-day cycles for rituximab), and a 5-year follow-up period. The safety follow-up visit (EOT visit) after treatment discontinuation is defined as 90 days after last treatment. The total duration is up to approximately 6 years per participant. The total study duration from FPFV to LPLV is expected to be approximately 8 years.

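### Protocol 9.4 ends active SAE seeking at the EOT visit, which now comes before most of the 90-day post-dose safety window, so it contradicts the protocol's own collection rules

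*Protocol*

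**What the plan says.** Protocol 9.4 contains two rules. Its first paragraph requires reporting, within 24 hours and whatever the suspected cause, of "all SAEs occurring after the participant has signed the ICF through completion of the study", or until new anticancer therapy if that comes first. It allows for exceptions specified elsewhere in the protocol. Its second paragraph states: "Investigators are not obligated to actively seek SAE information after the EOT visit". For SAEs learned of after that point, the duty to notify is stated for the case where "he/she considers the event to be reasonably related to the study treatment or study participation".

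The timing of EOT is set in Protocol 8.8: "The EOT visit will be performed at the time the decision is made to discontinue study treatment", or once the participant has "completed the prescribed treatment regimen (Cycle 12 Day 28"). A separate safety follow-up visit comes 90 days (± 7) after EOT (Protocol 8.9.1 and Table 3).

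The safety analysis uses a window that runs well past EOT. Protocol 8.3 says that adverse events "will be recorded from signing the ICF until 90 days after the last dose of treatment", or until new anticancer therapy. Protocol 10.4.2 counts as treatment-emergent any event up to and "within 90 days of the last administration of study treatment", and SAP 8.2.1 uses the same window.

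SAP 4.1.5 still treats the two visits as one: "The safety follow-up visit (EOT visit) after treatment discontinuation is defined as 90 days after last treatment".

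**The concern.** Serious and fatal treatment-emergent events are tabulated over the 90-day window whether or not they are judged related (SAP 8.2.4), and SAEs and deaths are central to the IDMC's review (Protocol 5.6). Section 9.4 is where a site looks for its SAE duties. Its second paragraph sets the cut-off at a visit that now comes near the start of the 90 days, not at their end.

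Two things are at stake. With approximately 275 centers, some may follow 9.4 and stop asking at EOT, while others follow 8.9.1 and collect for 90 more days. In addition, investigators' judgments of relatedness could filter SAEs that feed tables meant to ignore causality.

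Second primary malignancies show the same conflict over a longer period. Protocol 9.2 treats secondary malignancies as always serious, 9.5.1 lists second primary malignancy as an event of special interest for both tafasitamab/placebo and lenalidomide, and 8.3 requires follow-up for it throughout the study in participants who progress or stop early. The second paragraph of 9.4 makes no exception for it.

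**Working it through.** **Inputs.** 28-day cycles; last scheduled lenalidomide dose on Cycle 12 Day 21 and last tafasitamab/placebo dose on Cycle 12 Day 15 (Protocol 6.1); EOT on Cycle 12 Day 28 for completers (8.8), ± 2 days (Table 3); window end = last dose + 90 days (10.4.2, SAP 8.2.1); safety visit = EOT + 90 ± 7 days (8.9.1, Table 3). Study day = (cycle − 1) × 28 + day.

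**Step 1: the 9.4 rule with EOT as SAP 4.1.5 describes it.**
- Last lenalidomide dose: 11 × 28 + 21 = Day 329.
- Window closes: 329 + 90 = Day 419.
- EOT at 90 days after the last dose is also Day 419, so 0 days of the window follow it. On that timing the sentence cuts off none of the window.

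**Step 2: the same rule with EOT as Protocol 8.8 sets it.**
- Completer: EOT = 11 × 28 + 28 = Day 336. Days after EOT = 419 − 336 = 83, and 83/90 = 92%. The ± 2-day window gives 81 to 85 days.
- Completer whose last dose is tafasitamab/placebo on Day 323 (11 × 28 + 15): the window closes on Day 413, and 413 − 336 = 77 days follow EOT.
- Early discontinuer: days after EOT = 90 − (EOT day − last-dose day). This is all 90 if EOT falls on the day of the last dose, and fewer if the last dose was earlier.

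**Step 3: the cut-off moved to the safety follow-up visit.**
- Completer: 336 + 90 = Day 426 (419 to 433), at or after the Day 419 window end, so 0 days are lost.
- With EOT 2 days early and the visit 7 days early: 334 + 83 = Day 417, so 2 days are lost.
- Early discontinuer with EOT on the last-dose day and the visit 7 days early: 90 − 83 = 7 days.

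**Step 4: the passages side by side.**

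| Place | Duty after EOT | Runs to | Related events only? |
|---|---|---|---|
| Protocol 9.4, paragraph 1 | report all SAEs | study completion or new anticancer therapy | no |
| Protocol 9.4, paragraph 2 | no active seeking; notify if learned of | not stated | yes, as worded |
| Protocol 7.1.2 | follow for safety | follow-up visit, or later if related toxicities persist | no, up to the visit |
| Protocol 8.3 | record adverse events | 90 days after last dose or new anticancer therapy | no |
| Protocol 8.9.1, Table 3 | try to bring the participant back; collect adverse events | safety visit, 90 days after EOT | no |
| Protocol 10.4.2, SAP 8.2.1 | count as treatment-emergent | 90 days after last dose | no |

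Only paragraph 2 of 9.4 uses EOT as a cut-off.

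**Step 5: origin.** The Amendment 7 summary says that text placing EOT 90 days after the last dose was removed because that interval belongs to the safety visit alone. SAP 4.1.5 still carries the old equation. Protocol 2.2.3 still relies on collection at EOT to detect late effects, which also fits the old timing. The log serves here only to explain where the sentence may come from.

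**The case against.** The strongest reply is that the protocol as a whole does ascertain the window. Sections 7.1.2, 8.3 and 8.9.1 and Table 3 require collection through the 90-day visit. Section 8.3.1 and the reporting instructions at the end of 9.4 ask for SAEs within 24 hours with no EOT limit and no relatedness filter. Paragraph 2 never says that a known, unrelated SAE may go unreported. Deaths would surface anyway through 12-weekly survival follow-up (8.9.3), which records the reason for death (10.4.1.2.3).

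Much of this stands. A reader might infer that the 90 days are left without active ascertainment, but that is true only if paragraph 2 is read alone. The reply does not remove the contradiction, though. Because paragraph 1 of 9.4 allows for exceptions specified elsewhere, a site can take paragraph 2 as the exception.

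Other stronger readings also fail:
- *SAEs will be under-reported, most of all in early discontinuers because their risk is highest.* The documents give no SAE rate after EOT, overall or by time of stopping. The day counts are shares of calendar time, not of missed events. For anyone who starts new anticancer therapy within the 90 days they are upper limits, because 8.3 stops collection there.
- *The comparison of arms is biased.* The rule is the same in both arms of a blinded trial, and nothing shows a differential effect.
- *EOT is the day treatment ends.* For completers it is 7 days after the last scheduled lenalidomide dose and 13 days after the last tafasitamab/placebo dose.
- *SAP 4.1.5 corrupts the treatment-emergent counts.* Those are defined from the last dose. The effect is narrower: SAP 8.2.2 can censor the duration of non-serious events of special interest at 90 days after EOT, which with the 4.1.5 definition would mean 90 + 90 = 180 days after the last dose, before truncation at cut-off, discontinuation or death.

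**Conclusion.** The point holds as an internal contradiction about how SAEs are collected after EOT. Paragraph 2 of Protocol 9.4 cannot be reconciled with paragraph 1, with 7.1.2, 8.3, 8.9.1 and Table 3, or with the 90-day treatment-emergent definition. On the nominal schedule, with lenalidomide taken to Cycle 12 Day 21, 83 of the 90 post-dose days (92%) fall after EOT for a completer; for an early discontinuer it is up to all 90.

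The consequence is a risk of uneven collection between sites, mainly of non-fatal SAEs not judged related. The size of any undercount cannot be computed from the documents. That the sentence is left over from the former EOT timing is an inference, though a well-supported one. The primary efficacy analysis is not affected. The correction should be made because it is nearly free and makes the safety data more complete.

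**What to change.** In Protocol 9.4, paragraph 2:
1. Replace *after the EOT visit* by *after the 90-day safety follow-up visit*. Adding *or 90 days after the last dose, whichever is later* would also cover the few days that can be lost when that visit is held early.
2. State that the relatedness limit does not apply before that visit.
3. Reconcile the paragraph with paragraph 1 for the time after the visit. Changing the cut-off alone leaves paragraph 1 asking for all SAEs to study completion or new anticancer therapy and paragraph 2 asking only for related ones.
4. State that the second primary malignancy follow-up in 8.3 continues regardless.

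In SAP 4.1.5, define the EOT visit and the 90-day safety follow-up visit separately, and confirm that SAP 8.2.2 then reads as intended. Check the statement on late effects in Protocol 2.2.3 at the same time.

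The cost is a few sentences in the protocol, one in the SAP and a note to sites. The visit already exists and adverse events are already scheduled for collection there, so steps 1 and 2 add no procedure. Step 3 may change site workload after the visit, depending on which rule the sponsor confirms.

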9.5. Events of Clinical Interest

An ECI is an AE that is either serious or nonserious that must be documented in a certain manner for further evaluation and assessment.

9.5.1. Adverse Events of Special Interest by eCRF

Adverse events of special interest are defined as a subset of ECIs that an investigator should urgently communicate information about the event to the sponsor/designee for further evaluation. Communication can be in the form of eCRF entry, email, or phone call to the sponsor/designee.

Adverse events of special interest for tafasitamab/placebo are TLS, IRRs and allergic reactions to study drug ≥ Grade 3, CRS, SPM, hepatitis B reactivation, and PML.

Adverse events of special interest for lenalidomide are second primary malignancy.

Adverse events of special interest will be captured in the eCRF and if any of the serious criteria is met, should be captured as an SAE as well.

Adverse events of special interest should be reported as a diagnosis and should include the symptoms of the event as 1 event term. For example, IRR with symptoms of hives, chills, and fever.

9.5.2. Adverse Events of Special Interest by Category and Preferred Term

A second method will be used to identify AESIs programmatically using standardized MedDRA queries, custom MedDRA queries, and/or selected preferred terms. The same high-level terms as

described in Section 9.5.1 will be used for this analysis; please refer the SAP for further specific details.

9.6. Emergency Unblinding of Treatment Assignment

In case of a medical emergency, for a participant's safety management, the procedure for emergency unblinding is provided in the IRT or Study Reference Manual. This option may be used *only* if the participant's well-being requires the investigator to be aware of the participant's treatment assignment. If a participant's treatment assignment is unblinded, the sponsor or its designee must be notified immediately by telephone.

If an investigator, the site personnel performing assessments, or a participant is unblinded, then the participant must discontinue study treatment, unless there are ethical reasons to have the participant remain on the study treatment. In these cases, the investigator must obtain specific approval from the sponsor's (or its designee's) medical monitor for the participant to continue in the study.

9.7. Pregnancy

Pregnancy, in and of itself, is not regarded as an AE unless there is suspicion that the study treatment may have interfered with the effectiveness of a contraceptive medication or method. When a pregnancy has been confirmed in a participant during maternal or paternal exposure to study treatment, the following procedures should be followed in order to ensure safety:

- The study treatment must be interrupted immediately (female participants only).
- If the female participant is no longer pregnant and meets the treatment continuation criteria within 28 days of the scheduled start of a cycle study treatment may be resumed after approval has been received from the sponsor medical monitor.
- The investigator must complete and submit the Incyte Clinical Trial Pregnancy Form to Incyte Pharmacovigilance within **24 hours** of learning of the pregnancy.

Data on fetal outcome are collected for regulatory reporting and drug safety evaluation. Follow-up should be conducted for each pregnancy to determine outcome, including spontaneous or voluntary termination, details of the birth, and the presence or absence of any birth defects, congenital abnormalities, or maternal and/or newborn complications, by following until the first well-baby visit. Pregnancy should be recorded on a Clinical Trial Pregnancy Form and reported by the investigator to the sponsor or its designee. Pregnancy follow-up information should be recorded on the same form and should include an assessment of the possible causal relationship to the sponsor's study drug to any pregnancy outcome, as well as follow-up to the first well-baby visit or the duration specified in local regulations, whichever is later. Refer to the Incyte Reference Guide for Completing the Clinical Trial Pregnancy Form or Study Reference Manual.

Any SAE occurring during pregnancy of a study participant must be recorded on the Serious Adverse Event Report Form and submitted to the sponsor or its designee.

Abnormal pregnancy outcomes (eg, spontaneous abortion, fetal death, stillbirth, congenital anomalies, or ectopic pregnancy) are considered SAEs (if occurring in the study participant) and must be reported as described in Section 9.4. If an abnormal pregnancy outcome is reported in a

study participant's partner, the event should be reported to the sponsor on the Clinical Trial Pregnancy Form.

9.8. Warnings and Precautions

Special warnings or precautions for the study drug/treatment, derived from safety information collected by the sponsor or its designee, are presented in the IB. Additional safety information collected between IB updates will be communicated in the form of Investigator Notifications. Any important new safety information should be discussed with the participant during the study as necessary. If new significant risks are identified, they will be added to the ICF.

9.9. Product Complaints

The sponsor collects product complaints on study drugs and drug delivery systems used in clinical studies in order to ensure the safety of study participants, monitor quality, and facilitate process and product improvements.

All product complaints associated with material packaged, labeled, and released by the sponsor or its designee will be reported to the sponsor. All product complaints associated with other study material will be reported directly to the respective manufacturer.

The investigator or his/her designee is responsible for reporting a complete description of the product complaint via email or other written communication to the sponsor contact or respective manufacturer as noted in the packaging information. Any AE associated with a product complaint should be recorded as described in Section 9.3.

If the investigator is asked to return the product for investigation, he/she will return a copy of the product complaint communication with the product.

In Japan, complaints associated with unapproved medical devices will be reported to the sponsor with a Medical Device Defect Report Form, and the sponsor will report medical device defects to the PMDA as per local regulatory requirements.

9.10. Treatment of Overdose

The sponsor is not recommending any specific treatment of a suspected overdose of tafasitamab, rituximab, and/or lenalidomide. In case an overdose of tafasitamab, rituximab, and/or lenalidomide happens and requires treatment, symptomatic treatment including but not limited to blood product transfusions, growth factors, antibiotics, antiemetics, and analgesics may be administered per investigator's discretion.

For purposes of this study, overdose of tafasitamab/rituximab is defined as any tafasitamab/rituximab dose above 120% of the assigned dosage per single infusion as per Protocol.

For lenalidomide the overdose is defined as any dose greater than the planned dose for a particular participant as per Protocol.

Overdose is not an SAE unless it meets the criteria of an SAE (see Section 9.2).

In the event of an overdose, the investigator should do the following:

• Contact the medical monitor immediately.

- Closely monitor the participant for any AE/SAE and laboratory abnormalities as clinically appropriate.
- Document the quantity of the excess dose as well as the duration of the overdose in the eCRF.

Decisions regarding dose interruptions or modifications will be made by the investigator in consultation with the medical monitor based on the clinical evaluation of the participant.

